4.2 Demographic and baseline characteristics

Demographic variables are detailed below:

- Sex: Male/Female
- Age (in years), defined as:

(year of informed consent – year of birth)

- Age (in years) <35, 35-<50, ≥50
- Race: Asian (Japanese/Other Asian), White, Black or African American, American Indian or Alaska Native, Native Hawaiian or Other Pacific Islander
- Race: Japanese/Non-Japanese
- Ethnicity: Hispanic or Latino, Non-Hispanic or Latino.
- Weight (kg)

- Height (cm)
- BMI (kg/m²)
- Baseline CDAI: ≤330; > 330.
- Baseline PRO2: ≤24; > 24.
- Baseline SES-CD: ≤15; > 15.
- Proclivity to hypohepatia: Yes, No
Having a proclivity to hypohepatia is defined as having at least one baseline AST or baseline ALT value greater than the upper lab limit of the corresponding parameter.
- Baseline eGFR: (mL/min/1.73m²), defined as:

for males:

$$194 * \text{serum creatinine}^{-1.094} * \text{age}^{-0.287}$$

for females:

$$194 * \text{serum creatinine}^{-1.094} * \text{age}^{-0.287} * 0.739$$

- Baseline eGFR: (mL/min/1.73m²) <30, 30-<60, 60-<90, ≥90

Variables related with history of Crohn's disease presented below will be descriptively summarized by treatment group:

- Type of Crohn's disease: Small intestine-type, Small and large intestine-type, Large intestine-type, Other.
- Site of lesions: Gastroduodenum, Jejunum, Ileum, Cecum, Ascending colon, Transverse colon, Descending colon, Sigmoid colon, Rectum, Anus/perianal.
- Duration of Crohn Disease's (in years), defined as:

(Informed consent date – Crohn's disease onset date + 1)

365.25

- Duration of Crohn Disease's (in years): ≤5 years; > 5 years.
- Crohn Disease's related Surgical procedure (Yes/No)
- Type of surgical procedure: Endoscopic dilatation, Strictureplasty, Ileocolic side-to-side anastomosis, End-to-end anastomosis, Ileocolic segmental resection, Drainage Seton, Ilco pouch-anal anastomosis, Other.
- Surgical site: Gastroduodenum, Jejunum, Ileum, Cecum, Ascending colon, Transverse colon, Descending colon, Sigmoid colon, Rectum, Anus/perianal, Other.

Medical history defined as any comorbidities or Crohn's Disease's complications at the time of Informed Consent will be also analyzed. This information will be coded using the version of Medical Dictionary for Regulatory Activities (MedDRA) currently in effect at Linical at the time of database lock.

4.3 Prior or concomitant medications

All medications will be coded using the World Health Organization-Drug Dictionary (WHO-DD) version in use at the time of the DBL.

Prior medications are those the patient used before the first investigational medicinal product (IMP) intake. Prior medications can discontinue before first administration or can be ongoing during treatment phase.

Prior biologic treatment of Crohn's disease will be analyzed separately. Patients will be categorized depending on the prior biologic treatment used of Crohn's disease:

- Previous biologics: Yes; No.
- Prior biologic treatment used of Crohn's disease: Biologic naïve (no prior biologic treatment reported), 1 prior biologic failure (one prior biologic treatment reported), 2 prior biologic failures (2 prior biologic treatments reported), ≥ 3 prior biologics failures (3 or more prior biologic treatments reported)

Concomitant medications are any treatments received by the patient concomitantly to the IMP, from the first IMP intake to the end of treatment + 14 days. A given medication can be classified both as a prior medication and as a concomitant medication.

The following medications will be analyzed:

- Corticosteroids concomitant before randomization: Yes; No.
- Immunomodulators concomitant before randomization : Yes; No.
- Enteral nutrition concomitant before randomization : Yes; No.

4.4 Extent of investigational medicinal product exposure and compliance

Duration of IMP exposure is defined as date and time of last IMP administration – date and time of first double-blind IMP administration + 14 days, regardless of unplanned intermittent discontinuations. Duration will be presented in days.

4.5 Efficacy endpoints

4.5.1 Primary Endpoints for Efficacy

- CR100 response rate at Week 12, defined as ratio of patients who had CDAI reductions of at least 100 points from baseline to Week 12. CDAI score will be considered as collected in the eCRF by the investigator.

4.5.2 Secondary Endpoints for Efficacy

- CR70 response rate, CR100 response rate (excluding Week 12) and CDAI remission rate (proportion of subjects with below 150 points) at each evaluation time
- Proportion of subjects with at least 5-point reduction in PRO2 from baseline (PRO2-CR5 response rate), proportion of subjects with at least 8-point reduction from baseline (PRO2-CR8 response rate), and proportion of subjects with below 8 points (PRO2-remission rate) at each evaluation time
- Proportion of subjects with at least 50% improvement in SES-CD score from prior to IMP administration (endoscopic response rate) and proportion of subjects with 2 or less in SES-CD score (endoscopic remission rate) at Week 12
- Change and percent change in CDAI score from baseline at each evaluation time
- Change and percent change in PRO2 from baseline at each evaluation time
- Change and percent change in SES-CD score from baseline at Week 12
- In subjects who were concomitantly taking adrenocorticosteroid at remission induction period, proportion of subjects who achieved steroid-free maintenance (steroid-free remission rate, steroid-free improvement rate) through steroid dose reduction and clinical remission (CDAI remission or PRO2 remission) or clinical improvement (CR70 response, CR100 response, PRO2-CR5 response or PRO2-CR8 response)
- In subjects who were concomitantly taking adrenocorticosteroid at remission induction period, dosage (mg/day), change and percent change of adrenocorticosteroid from baseline.

4.6 Safety endpoints

Assessment items for safety evaluation include the following:

- Adverse events
- Laboratory test values
- Vital signs, weight, physical examination
- Standard 12-lead ECG examinations, neurological symptoms
- Blood CD4⁺ cell count

4.7 Quality of Life or other Patient Report Outcomes endpoints

ePRO of "4.5.2 Secondary Endpoints for Efficacy" is applicable.

4.8 Pharmacokinetic Parameters endpoints

Individual serum concentration values of E6011 will be summarized as follows:

- Pharmacokinetics and serum E6011 concentration
 - Individual serum concentration values of E6011 will be listed and summarized using descriptive statistics (n, mean, standard deviation, geometric mean, CV, geometric CV, median, Q1, Q3, minimum and maximum) and nominal time point. The data of time points in subject with interruption will not be included on calculation of summary statistics after the interruption.
 - Actual sampling time and serum concentrations of E6011 for each subject will be listed.
 - The individual serum E6011 concentration–time profile will be displayed in linear and semi–log scales using actual sampling times in the same graph.
 - The mean serum concentrations of E6011 will be displayed using nominal blood sampling times with standard deviation in linear and semi–log scales in the same graph.

4.9 Immunogenicity endpoints

Individual serum concentration values of anti-E6011 antibody will be summarized as follows:

- Actual sampling time and serum concentrations of anti-E6011 antibody for each subject will be listed.
- The frequency and rate of serum anti-E6011 antibody and E6011-induced anti-E6011 antibody expression at each evaluation time will be calculated for each treatment group. If anti-E6011 antibodies and E6011-induced anti-E6011 antibody are confirmed, the frequency and ratio of their neutralizing activity (if present) and isotypes are to be calculated.

4.10 Biomarker endpoints

Individual serum concentration values of serum total fractalkine concentration (FKN), faecal calprotectin and serum CRP will be summarized as follows:

- Individual serum concentration values of fractalkine concentration (FKN), faecal calprotectin and serum CRP will be listed and summarized using descriptive statistics (n, mean, standard deviation, geometric mean, CV, geometric CV, median, Q1, Q3, minimum and maximum) and nominal time point. The data of time points in subject with interruption will not be included on calculation of summary statistics after the interruption.
- Actual sampling time and serum concentrations of fractalkine concentration (FKN), faecal calprotectin and serum CRP for each subject will be listed.

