#### <Neurological symptoms>

Subjects are to be assessed for the presence or absence of neurological symptoms using the neurological symptoms checklist (Attachment 13) when indicated by the study schedule (Table 4), and the results are to be recorded in case report forms. Also, if a neurological symptom is suspected whenever subjects are examined outside of specified assessment times, a neurological assessment must be performed using the neurological symptoms checklist. Any abnormalities that are found after IMP administration must be reported to the Sponsor using the "Neurological Symptoms Report (Attachment 14)" sent by FAX, etc. and examined by a neurologist or other specialists. Additionally, brain MRI (T1-weighted, FLAIR and diffusion-weighted imaging) is to be performed within two weeks and the MRI images submitted to the Sponsor. The Sponsor shall immediately forward the information to a PML evaluator and seek advice on whether the subject should continue the IMP administration. The IMP administration is to be put on hold until the evaluation is completed by the PML evaluator. Such events are to be documented in case report forms as AEs.

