# 9.7.1.2 Definition of the analysis population

FAS (full analysis set) is a set of subjects to whom the IMP has been administered after randomisation, and who had 1 or more evaluable, post-IMP administration primary efficacy endpoint data points.

PPS (per protocol set) is a set of subjects who satisfactorily complied with the Protocol. Detailed

criteria deemed to match present analysis sets are to be decided upon before the database is locked and unblinded, and they are to be specified in the analysis plan.

Safety analysis set is a set of subjects to whom the IMP has been administered, and who had 1 or more evaluable, post-IMP administration safety data.

Pharmacokinetic analysis set is a set of subjects to whom the IMP has been administered, and who had 1 or more evaluable, post-IMP administration serum E6011 concentration data points.

Pharmacodynamic analysis set is a set of subjects to whom the IMP has been administered, and who had 1 or more evaluable, post-IMP administration biomarker data points.

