# 9.7.1.7.2 Analysis of pharmacodynamics, pharmacogenomics/pharmacogenetics and other biomarkers

Exploratory biomarker and pharmacogenomic analyses are to be performed using the pharmacodynamic analysis set. Summary statistics for serum total FKN concentration, measured faecal calprotectin and serum CRP values, change and percent change from baseline are to be calculated by treatment group and evaluation time.

Details and results of the analysis of blood CD16+ monocytes, etc., genetic marker for CD16+ monocytes, etc. and blood biomarkers (comprehensive proteome analysis) using the residual serum

collected for this study will be provided in a separate report and will not be included in the Clinical Study Report.

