5.4 Pharmacodynamic Analysis Set

The **pharmacodynamic analysis set** will be defined as all available data on patients who took the active treatment and who had 1 or more evaluable, post-IMP PD biomarker data points.

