6.10.3 Biomarker and Pharmacogenomic Parameters

Exploratory biomarker and pharmacogenomic analyses are to be performed using the pharmacodynamic analysis set. Summary statistics for serum total FKN concentration, measured faecal calprotectin and serum CRP levels, change and % change from baseline are to be calculated by treatment group and evaluation time.

CCI

Details and results of the analysis of blood CD16⁺ monocytes, etc. and blood CD16⁺ monocytes etc. genetic markers are to be reported in a separately created report, and not included in the Clinical Study Report

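### SAP 4.10 drops biomarker values from summary statistics after an undefined interruption; the rule is not in the protocol, is not declared in SAP 6.11, and may bias the exploratory by-arm summaries

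*SAP*

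**What the plan says.** SAP 4.10 (Biomarker endpoints) provides descriptive statistics for FKN, faecal calprotectin and CRP by nominal time point, then adds: "The data of time points in subject with interruption will not be included on calculation of summary statistics after the interruption". SAP 4.8 has the identical sentence for serum E6011. Neither section defines an interruption. SAP 4.10 does keep every value visible by subject: "Actual sampling time and serum concentrations of fractalkine concentration (FKN), faecal calprotectin and serum CRP for each subject will be listed".

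The protocol's biomarker analysis (9.7.1.7.2) covers FKN and the other two markers without any exclusion: "measured faecal calprotectin and serum CRP values, change and percent change from baseline are to be calculated by treatment group and evaluation time". Its population (9.7.1.2) is equally broad: "Pharmacodynamic analysis set is a set of subjects to whom the IMP has been administered, and who had 1 or more evaluable" biomarker results after dosing. The protocol counts placebo as IMP (9.5.1.5.1).

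Elsewhere in the SAP:
- Section 6.10.3 repeats the protocol analysis by treatment group and time, without the rule: "Exploratory biomarker and pharmacogenomic analyses are to be performed using the pharmacodynamic analysis set".
- Section 5.4 defines that set as "all available data on patients who took the active treatment and who had 1 or more evaluable, post-IMP PD biomarker data points".
- Section 6.9.2 lists CRP among the laboratory parameters, summarised by treatment and time point with no exclusion.
- Section 6 undertakes to document differences from the protocol, and 6.11 reports none.

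**The concern.** Interruption happens after randomisation and may be related to tolerability or disease course. The protocol itself provides for one kind. After an abnormal neurological finding, "The IMP administration is to be put on hold until the evaluation is completed by the PML evaluator". If interruptions differ between arms, or if interrupted patients have different marker levels, a summary restricted to uninterrupted time no longer describes the randomised groups.

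Three features add to this. As worded, the exclusion has no end: nothing returns a patient's values to the tables once dosing resumes. No matching exclusion applies to CDAI, PRO2 or SES-CD in SAP 6.8, so clinical and biomarker results at the same visit could describe different patients. And because the term is undefined, a missed dose, a held dose or a paused infusion might each qualify, which leaves a choice to be made with data in hand. Protocol 9.7.2 gives 25 enrolled subjects, so each such choice carries weight.

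**Working it through.** The plan states no figure on this point, so there is none to reproduce. The check is a comparison of texts followed by an illustration of size.

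**Comparison of texts**

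| Place | Exclusion after interruption? | Population |
|---|---|---|
| Protocol 9.7.1.2, 9.7.1.7.2 | No | All IMP-treated with a post-dose biomarker value |
| SAP 4.10 | Yes, from summary statistics only | Not stated |
| SAP 5.4, 6.10.3 | No | Patients who took active treatment; summaries by treatment group |
| SAP 6.9.2 (CRP only) | No | Safety analysis set |
| SAP 6.11 | No modification declared | – |

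SAP 4.10 therefore adds a rule that the protocol lacks and the SAP does not declare. If any patient is interrupted, the report could show two CRP summaries for one visit with different numbers of patients.

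**Which visits are exposed**

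In the double-blind period calprotectin is sampled at Weeks 0, 2, 4, 8 and 12 (SAP 6.6.2), which gives 4 post-baseline visits. Dosing follows the day's assessments. If a missed Week 2 dose counts as an interruption, Weeks 4, 8 and 12 drop out: 3 of 4. FKN is scheduled only for Weeks 0 to 12 and at discontinuation. After Week 12 every continuing patient receives open-label E6011, so later visits carry no placebo contrast.

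**Illustrative size**

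Inputs:
- Enrolled: 25 (protocol 9.7.2). An even 1:1 split, assumed because the actual split is not given, is 12 and 13.
- *f*: share of an arm interrupted. Not in the documents; assumed.
- *d*: excess of the log marker in interrupted patients. Not in the documents; assumed 0.7 (about 2-fold) or 1.1 (about 3-fold).

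One patient is 1/13 = 7.7% to 1/12 = 8.3% of an arm. That is a patient's weight, not a bias.

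Set the log mean of uninterrupted patients in an arm to 0. With all values kept, the arm's log mean is *f·d*; with the exclusion it is 0. The E6011/placebo geometric mean ratio is therefore multiplied by exp[−(*f*₁*d*₁ − *f*₂*d*₂)], where 1 is E6011 and 2 is placebo.

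| *f*₁ v *f*₂ | *d* (both arms) | Multiplier |
|---|---|---|
| 10% v 10% | 0.7 | exp(0) = 1.00 |
| 25% v 5% | 0 | exp(0) = 1.00 |
| 10% v 20% | 0.7 | exp(0.07) = 1.07 |
| 20% v 10% | 0.7 | exp(−0.07) = 0.93 |
| 5% v 25% | 1.1 | exp(0.22) = 1.25 |
| 25% v 5% | 1.1 | exp(−0.22) = 0.80 |

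Equal rates do not guarantee 1.00. With 15% in each arm but *d*₁ = 0 and *d*₂ = 1.1, the multiplier is exp(0.165) = 1.18.

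A 5% share is less than one patient in an arm of 12 or 13. The nearest whole-patient case, 1 of 13 on E6011 v 3 of 12 on placebo with *d* = 1.1, gives exp[1.1 × (0.250 − 0.077)] = exp(0.190) = 1.21. These are examples, not bounds: none v 3 of 12 gives exp(0.275) = 1.32.

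**The case against.** The strongest reply is that the rule does little harm. The values are listed. The analyses are exploratory and descriptive, with no between-arm test or estimate of these markers specified. CRP has an unrestricted table. The scheduled neurological checklist in the double-blind period falls only at screening, Week 12 and discontinuation, so an earlier hold would need an unscheduled suspicion. All of this stands, and it keeps the point minor. It does not help calprotectin or FKN, which have no by-arm summary that clearly escapes the rule.

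There is also a positive case for FKN. Total FKN includes the E6011–FKN complex (protocol 9.4.4), so it depends on exposure, and SAP 6.10.5 plots biomarker and E6011 profiles on one graph. If the exclusion stays in 4.8 and leaves 4.10 entirely, different patients could lie behind the two curves. This supports an uninterrupted view as a supplement. It does not support making that view the only calprotectin summary, or leaving it undeclared.

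A reader might infer more than the documents support:
- That the SAP discards biomarker data. It does not: only summary statistics are affected, and only after the interruption.
- That the sentence was carried over from the PK section by mistake. Identical wording does not show that.
- That SAP 5.4 promises all available data for everyone. The same sentence restricts the set to patients who took active treatment, which is a separate conflict with the protocol's set and with summaries by arm.

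**Conclusion.** The point holds as an undefined and undeclared departure from the protocol that may bias exploratory by-arm summaries, mainly calprotectin and FKN up to Week 12. It does not touch the primary endpoint.

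A reader might go further and conclude that the comparison is biased. The documents do not show this: they give no interruption rate and no marker levels in interrupted patients. The multiplier is 1.00 if interruption is equally frequent and equally selective in both arms, or unrelated to the marker. In the other cases tabulated it runs from 0.80 to 1.25, in either direction, and that range rests wholly on assumed inputs.

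The reading assumes that interruption means interruption of dosing, which is likely but unstated. The comparison is with protocol version 11.0; SAP section 6 cites version 10, which was not available for this check.

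**What to change.** 1. In SAP 4.10, remove the exclusion from the main biomarker summaries. Summarise all observed FKN, calprotectin and CRP values by treatment group and evaluation time, as in protocol 9.7.1.7.2, and flag post-interruption values in the existing listing. The sentence can stay in 4.8 for serum E6011.
2. If an uninterrupted-dosing view is wanted, for example FKN beside E6011 in 6.10.5, define interruption for analysis purposes. Show that view as a supplementary table with the number excluded per arm and visit, and declare it in 6.11.
3. Reconcile the active-treatment wording of SAP 5.4 with the protocol's pharmacodynamic set so that the placebo arm is included. Without this, deleting the sentence in 4.10 does not by itself secure summaries by arm.

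The cost is a small SAP edit and at most one extra table. No new data are needed. The edit belongs before the relevant database lock, when protocol 9.7 requires the analysis plan to be fixed.

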5 ANALYSIS POPULATIONS

5.1 Efficacy Populations

FAS (full analysis set) is a set of subjects to whom the IMP has been administered after randomization, and who had 1 or more evaluable, post-IMP administration primary efficacy endpoint (i.e., to have an evaluable CDAI value at baseline and any other post baseline).

PPS (per protocol set) is a set of subjects who has been randomized and satisfactorily ended the remission induction treatment period, subjects that fulfill all inclusion /exclusion criteria and have no major or critical protocol violations.

Patients in the efficacy populations will be analyzed according to the treatment group allocated by the randomization even if not treated with the correct treatment assigned.

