#### Analysis of primary endpoint

For Week 12 CR100 rate, the Bayesian posterior distribution of the difference in the CR100 rate at Week 12 between the E6011 group and the placebo group is to be calculated. If there was a 50% or more probability of the difference between both groups being 25% or more, the efficacy of E6011 is confirmed.

Noninformative prior distribution is to be used for both the E6011 group and the placebo group.

Subjects with missing primary endpoint data by Week 12 after administration due to premature discontinuation or other reasons are treated as treatment failures (non-responder imputation [NRI]).

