6.8.1 Primary Efficacy analysis

Primary analysis aims to determine if the treatment effect in CR100 response rate at Week 12 is expected to be higher for patients treated with E6011 than for patients treated with placebo.

The Bayesian posterior distribution of the difference in the CR100 rate at Week 12 between E6011 (p1) and placebo (p2) is obtained as p1-p2 posterior distributions. Non-informative prior (Jeffreys) Beta (1/2, 1/2) distributions described by (Oleksandr Sverdlov, Yevgen Ryeznik, & Sheng Wu, January 1, 2015) will be used to calculate p1 and p2 posterior distributions.

A MCMC algorithm will be performed using the following parameters:

- Number of chains = 3
- Initial values for the algorithm in every chain= 3 starting values simulated by a Beta (0.5, 0.5)
- Number of Burn-in = 100000

- Number of Iterations = 200000

Diagnostic for the MCMC convergence will be checked through the Geweke Diagnostics test, Raftery-Lewis Diagnostics, Gelman-Rubin convergence and the autocorrelation efficiency. In case of any issue due to an autocorrelation or non-convergence of the algorithm, the size of the burn-in, the number of iterations and a possible thinning will be evaluated.

Efficacy of E6011 will be confirmed if there was a 50% or more probability of the difference between both groups being 25% according to the posterior distribution.

Probability of the difference between groups being greater than zero will be also calculated.

Subjects with missing primary endpoint data due to premature discontinuation before 12 weeks after administration, or other reasons are treated as non-responders (NRI) in the modeling of the endpoint.

Primary analysis will be performed in the FAS population, and in the PPS population as a supportive analysis.

Two sensitivity analysis will be performed a Last Observation Carried Forward (LOCF) and an Observed Case (OC) imputation for CDAI at week 12 will be used instead of NRI.

Another supportive analysis will be performed following the same logistic regression model (randomization strata and treatment group as fixed factor) used in the secondary analysis.

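### The FAS drops treated patients with no evaluable post-baseline CDAI, so they leave the primary denominator instead of counting as non-responders

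*SAP*

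**What the plan says.** The FAS has two conditions. The first is treatment: SAP 5.1 describes it as "a set of subjects to whom the IMP has been administered after randomization", and protocol 9.7.1.2 says the same. The second is a measurement after dosing. The protocol asks for patients "who had 1 or more evaluable, post-IMP administration primary efficacy endpoint data points". The SAP explains this as needing "to have an evaluable CDAI value at baseline and any other post baseline".

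SAP 6.8.1 then gives the missing-data rule: "Subjects with missing primary endpoint data due to premature discontinuation before 12 weeks after administration, or other reasons are treated as non-responders (NRI". Protocol 9.7.1.6.1 has the same rule, and neither text makes an exception for patients without post-baseline data. But SAP 6.8.1 also states: "Primary analysis will be performed in the FAS population, and in the PPS population as a supportive analysis". NRI therefore reaches only patients who have already met the FAS conditions.

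The decision rule, in the protocol synopsis, is: "If there was a 50% or more probability of the difference between both groups being 25% or more, the efficacy of E6011 is confirmed". SAP 6.8.1 specifies "Non-informative prior (Jeffreys) Beta (1/2, 1/2) distributions" for the two arms.

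**The concern.** CR100 under NRI is a yes/no outcome that can be assigned to every treated patient. Someone with no Week 12 CDAI is a failure by rule, so no later measurement is needed to score that patient. Requiring one removes a patient whose outcome the plan has already defined.

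This can happen. In the study schedule the first planned post-baseline CDAI is at Week 2, after the Week 0 and Week 1 infusions. The discontinuation visit lists CDAI, but the schedule footnote asks only for as much of that visit as can be done. Protocol 9.5.1.3.1 leaves the CDAI uncalculated when three or more diary days are missing. A patient who stops after one or two infusions and does not return, or returns without a usable diary, may have no evaluable value at all.

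Whether that happens is determined after randomisation and may differ between arms. With 25 patients and a fixed threshold of 0.50, one denominator can decide the result.

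**Working it through.** **Who is excluded**

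| Treated patient | In FAS? | Scored under NRI? |
|---|---|---|
| Leaves before Week 2, calculable CDAI at discontinuation | Yes | Yes, failure |
| Week 2 CDAI not calculable, any later one calculable, Week 12 missing | Yes | Yes, failure |
| No evaluable CDAI at any time after baseline | No | No, absent from denominator |

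Only the third row is at issue. The other planned analyses do not bring that patient back. Last observation carried forward has no post-baseline value to carry, the observed-case analysis needs a Week 12 value, and the per-protocol set requires completion of induction.

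**Inputs.** Prior Beta(0.5, 0.5) per arm (SAP 6.8.1); margin 0.25 and threshold 0.50 (protocol synopsis); 20 per arm planned (SAP 8); 25 enrolled (protocol 9.7.2). The split of the 25 is not stated. I assume 12:13 or 13:12, written E6011:placebo, because allocation is 1:1. True response rates are also assumptions.

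**Formula.** With r responders out of n, an arm's posterior is Beta(0.5 + r, 0.5 + n − r). Then π = P(p1 − p2 ≥ 0.25) = ∫ f2(y)·[1 − F1(y + 0.25)] dy, where f2 is the placebo posterior density and F1 the E6011 posterior distribution function. Efficacy is confirmed if π ≥ 0.50. I evaluated π by numerical integration for every possible result.

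**The plan's own figure.** At 20 per arm and a true difference of 40 points, the chance of confirming is 80.7% (placebo rate 30%) to 87.4% (placebo rate 60%) over placebo rates of 5% to 60%. The stated figure of above 80% reproduces.

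**One E6011 patient removed, 12:13**
- Counted as a failure: 5/12 vs 2/13, Beta(5.5, 7.5) vs Beta(2.5, 11.5), π = 0.491, not confirmed.
- Excluded: 5/11 vs 2/13, Beta(5.5, 6.5) vs Beta(2.5, 11.5), π = 0.574, confirmed.

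**One placebo patient removed, 13:12**
- Counted as a failure: 8/13 vs 4/12, Beta(8.5, 5.5) vs Beta(4.5, 8.5), π = 0.537, confirmed.
- Excluded: 8/13 vs 4/11, Beta(8.5, 5.5) vs Beta(4.5, 7.5), π = 0.474, not confirmed.

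**How many results flip**

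| Split | E6011 patient removed: fail → pass | Placebo patient removed: pass → fail |
|---|---|---|
| 12:13 | 5 result pairs | 7 |
| 13:12 | 2 (11/13 vs 7/12; 12/13 vs 8/12) | 5 |
| 20:20 | 14 (e.g. 10/20 vs 5/20, 0.475 → 10/19 vs 5/20, 0.545) | 1 |

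**Chance of confirming, given one such E6011 patient.** That patient is fixed as a failure or excluded. The rest of the E6011 arm and the whole placebo arm respond at the assumed rates.

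| Split | True rates (E6011/placebo) | Excluded | NRI |
|---|---|---|---|
| 12:13 | 45%/20% | 47.2% | 37.2% |
| 12:13 | 20%/20% | 5.4% | 2.4% |
| 20:20 | 45%/20% | 51.1% | 37.1% |
| 20:20 | 20%/20% | 2.7% | 1.1% |

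At 13:12, removing an E6011 patient makes almost no difference at these rates. Removing a placebo patient there turns a confirmed result into an unconfirmed one with probability 5.3% at 45%/20%.

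**The case against.** The strongest reply is that the plan already protects against most of this. Protocol 9.3.3 and 9.5.5 require discontinuation assessments for everyone who stops after dosing, and the schedule lists CDAI there. One or two missing diary days are filled in, sites contact patients before each diary week, and incomplete entries are chased. One evaluable CDAI at any later time is enough for the FAS. All of this stands, and it makes the affected group small.

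Two stronger readings therefore fail. A reader might infer that the earliest dropouts in general escape the non-responder rule. They do not if a CDAI can be calculated at discontinuation. A reader might also infer that three missing diary days remove a patient. They remove that visit's CDAI only; the patient is lost only if no other evaluable value exists.

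The numerical examples are also boundary cases. At 12:13, with one E6011 failure removed, 5 of 12 × 14 = 168 possible results flip. The chance of a flip is 47.2 − 37.2 = 10.0 points at 45%/20% and 5.4 − 2.4 = 3.0 points at 20%/20%. These are conditional on such a patient existing.

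Finally, the protocol and SAP agree, patients are analysed as randomised, SAP 6.1 calls the analysis exploratory, and SAP 6.3 tabulates randomised, treated and FAS counts, so an exclusion would be visible. That is fair. But agreement between the documents means only that both need the edit, and a visible exclusion still leaves the primary decision resting on the reduced denominator.

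**Conclusion.** The point holds for a narrow group: randomised, treated patients with no evaluable CDAI at any time after baseline. For them the FAS definition overrides the NRI rule, and no planned analysis counts them as failures.

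If one such patient exists, the effect can matter. With an E6011 patient at 12:13, exclusion raises the chance of confirming efficacy from 37.2% to 47.2% at true rates of 45%/20%, and from 2.4% to 5.4% when both rates are 20%. The size depends on the assumed split and rates; at 13:12 an E6011 exclusion flips the decision only at very high response rates.

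The documents do not support the inference that the result has been changed or that the rule favours E6011. They report no such patient and no arm split, and excluding a placebo failure works against E6011. Nor is it fair to say that the randomised comparison is broken. The plan permits a post-randomisation exclusion that it does not need, and whose effect could decide a close result.

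**What to change.** In SAP 5.1 and protocol 9.7.1.2, define the primary analysis set as all randomised subjects who received at least one dose of IMP, analysed in the arm to which they were randomised. In SAP 6.8.1 and protocol 9.7.1.6.1, state that any subject in this set without an evaluable Week 12 CDAI is a CR100 non-responder. Keep the post-baseline CDAI requirement only for change-from-baseline summaries.

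A lesser alternative is to leave the FAS as it is and prespecify a sensitivity analysis in all randomised and treated subjects with NRI. That would show the effect but leave the primary decision on the reduced set.

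The cost is wording only, with no new data. The downside is a slightly lower response rate in an arm that has such a dropout. If there is none, the result is unchanged. The edit should precede lock and unblinding of the remission-induction database; if that has passed, the all-treated result should be reported alongside the planned one and labelled post hoc.
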